## **5.5. Derived and Transformed Data**

### **5.5.1. Study Day**

Study day is the day relative to the date of randomization. Day 1 is defined as the date of randomization. Assessments that occur after randomization but before the first dose of study drug are considered to occur on study Day 1.

Assessments without timestamp collected on the same date as the first date of study drug administration are considered to occur before the first dose of study drug administration.

For visits (or events) after randomization, day is calculated as:

- Study day = visit (or event) date - date of randomization + 1

For visits (or events) before randomization, day is calculated as:

- Study day = visit (or event) date - date of randomization

The quantity ‘days since first dose’ is defined as:

- days since first dose = visit (or event) date – date of first dose + 1

The quantity ‘days since last dose’ is defined as:

- days since last dose = visit (or event) date - date of last dose

For summaries that present distribution of time expressed in weeks and months, weeks are defined as days divided by seven and months as days divided by 30.4.

**Table 3: Analysis Visit Windows for On-Treatment**

Analysis Visit	Label	Target		Analysis Window
		Study Day a	Days After Last Dose	
0	Day 1 b	1	-	1
1	Week 1	7	-	$2 \leq \text{study day} \leq 10$
2	Week 2	14	-	$11 \leq \text{study day} \leq 21$
4	Week 4	28	-	$22 \leq \text{study day} \leq 35$
6	Week 6	42	-	$36 \leq \text{study day} \leq 49$
8	Week 8	56	-	$50 \leq \text{study day} \leq 70$
12	Week 12 c	84	-	$71 \leq \text{study day} \leq 98^d$

a Study Day is relative to the date of randomization (Section [5.5.1](#)).

b Day 1 is the last measurement prior to the first study drug administration.

c Week 12 is the end dosing interval.

d Data collected 2 or more days after last dose will be excluded from on treatment

### 5.5.3.1. Off-Treatment Visit Windows

Patients who permanently discontinue study drug prior to Week 12 are asked to resume the planned assessments according to the study schedule in the protocol. Off-treatment values for clinical laboratory evaluations (Section 9.5), vital signs (Section 9.6), and electrocardiograms (Section 9.8) are those that occur after the last dose date for patients permanently discontinuing study drug prior to Week 12 and is summarized relative to their last dose of study drug. Off-treatment safety assessments (clinical labs, vital signs, and electrocardiograms) are grouped for analyses according to the strategy in Table 4.

**Table 4: Analysis Visits for Off-Treatment assessments**

Off-Treatment Analysis Visit	Label	Target Study Day (days after last dose)	Analysis Window
3	Off Treatment Day 3 b	3	2 ≤ days after last dose ≤ 4
7	Off Treatment Day 7 b	7	5 ≤ days after last dose ≤ 10
14	Off Treatment Day 14 b	14	11 ≤ days after last dose ≤ 17
21	Off Treatment Day 21 b	21	18 ≤ days after last dose ≤ 24
28	Off Treatment Day 28 b	28	25 ≤ days after last dose ≤ 31
35	Off Treatment Day 35 b	35	32 ≤ days after last dose ≤ 38

a Last day of on-treatment for patients permanently discontinuing study drug prior or on to Week 12. Assessments that occur on the date of last dose or less than 2 days after last dose are considered on treatment and summarized using Table 3 windows.

b The off-treatment values indicate the value closest to the date of last dose.

### 5.5.4. Laboratory Evaluations Imputations

Any laboratory assessments less than the lower limit of detection (i.e., < LLD) are imputed as LLD/2. If no LLD is available, then the imputed value is the minimum numeric value listed divided by 2 (e.g., < 25 is 25/2=12.5). Laboratory assessments above the ULD are imputed as the ULD. If the lab result is qualitative but presented as > X and X is 10 times greater than the ULN or the ULN is not present, then the value X is used in the analysis.

### 5.5.5. Estimated Glomerular Filtration Rate (eGFR)

The eGFR is calculated using the formula below according to patient's age at the date of consent. The formula will not change throughout the study. The Chronic Kidney Disease Epidemiology Collaboration (CKD-EPI) equation is used for adult patients (age at consent at least 18 years):

- $eGFR (\text{mL/min/1.73 m}^2) = 141 \times \min(S_{\text{cr}}/\kappa, 1)^{\alpha} \times \max(S_{\text{cr}}/\kappa, 1)^{-1.209} \times 0.993^{\text{Age}} \times 1.018 \text{ [if female]} \times 1.159 \text{ [if black]}$

where  $S_{\text{cr}}$  is serum creatinine (mg/dL),  $\kappa$  is 0.7 for females or 0.9 for males, and  $\alpha$  is -0.329 for females or -0.411 for males. Min indicates the minimum of  $S_{\text{cr}}/\kappa$  and 1, and max indicates the maximum of  $S_{\text{cr}}/\kappa$  and 1.  $\text{Age}$  indicates age at time of serum creatinine collection as collected in CRF.

#### 5.5.5.1. Prognosis of CKD by eGFR and Albuminuria Category

Prognosis of CKD is determined by the intersection of the following eGFR and albuminuria categories (KDIGO 2012):

**Table 5: eGFR Category**

eGFR Category	eGFR (mL/min/1.73 m  )
1	≥ 90
2	60 to < 90
3a	45 to < 60
3b	30 to < 45
4	15 to < 30
5	< 15

**Table 6: Albuminuria Category**

UACR Category	UACR (mg/g)
1	< 30
2	30 to ≤ 300
3	> 300

#### 5.5.6. Urine Albumin to Creatinine Ratio (UACR)

UACR is provided in the central laboratory database as the ratio of urine albumin to urine creatinine from the first morning void (FMV) urine collection. The UACR value is reported in the central laboratory database as missing when the FMV urine albumin result is < LLD. Urine albumin results < LLD and the corresponding UACR missing values are imputed as follows:

- If urine albumin result = < LLD, then
  - Imputed urine albumin result (mg/dL) = LLD/2
  - Imputed UACR(mg/g) = (imputed urine albumin result in mg/dL) / [(urine creatinine in mg/dL) / 1000]

The UACR results are log-transformed for analysis to produce data that are more normally distributed. Any imputed UACR result where UACR=0 is considered to be 0.1 mg/g for purposes of calculating the geometric mean.

#### **5.5.6.1. Baseline Urine Albumin to Creatinine Ratio (UACR) Categorical Status**

Baseline UACR status will be grouped by the following categories using baseline UACR (see Section 5.4):

- UACR <=300 mg/g
- UACR > 300 mg/g

#### **5.5.6.2. eGFR Category used in Stratification**

There will be no multiple baseline eGFR categories used for stratification since the inclusion criteria is as such:

- 20 mL/min/1.73 m^2 <=eGFR < 60 mL/min/1.73 m^2

#### **5.5.6.3. UACR Category used in Stratification (UACR\_STRAT)**

The UACR category used for stratification (UACR\_STRAT) is determined by the randomization list with the following categories:

- UACR <= 300 mg/g
- UACR > 300 mg/g

#### **5.5.7. Electrocardiogram Fridericia Corrected QT Interval**

Electrocardiogram intervals are assessed locally at each site. The following formula is used to calculate the QTcF interval for analysis from QT and RR intervals:

$$\bullet \quad QTcF = QT / \sqrt[3]{RR}$$

where RR = 60 / (Heart Rate).

#### **5.5.8. Natural log(UACR)/eGFR**

To evaluate UACR after adjusting for filtration rate, ln(UACR)/eGFR (Sections 5.5.6 and 5.5.5) is assessed.

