#### **5.1.2.6. Increases in Urinary Protein**

Increases in urinary albumin have been observed in some patients treated with bardoxolone methyl with chronic kidney disease. The increases are likely due to bardoxolone methyl's pharmacological modulation of tubular protein reabsorption and have not been associated with interstitial fibrosis or injury. In preclinical studies, bardoxolone methyl has been shown to downregulate the primary proteins involved in protein reabsorption in the proximal tubules: the megalin-cubilin complex ([Reisman, 2012](#)). Moreover, the magnitude of observed eGFR increases with bardoxolone methyl treatment is thought to reduce the residence time of protein in the proximal tubules, thereby reducing protein reuptake and increasing urinary protein levels.

Therefore, increased eGFR, together with decreased megalin expression, is thought to result in decreased fractional absorption of albumin and increased urinary excretion of albumin.

Consistent with bardoxolone methyl-mediated protection in preclinical models of protein-overload-induced nephropathy, these pharmacological effects are thought to reduce protein overload and secondary nephropathy caused by excessive albumin uptake and therefore are not associated with tissue injury and interstitial fibrosis ([Rossing, 2019](#)).

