### **9.1.6. Management of Urinary Protein**

Although increases in urinary protein with bardoxolone methyl have not been associated with kidney injury or loss of kidney function, investigators should closely monitor patients if urinary albumin to creatinine ratios increase by more than 100% and exceed 1000 mg/g for proteinuria and should consult the medical monitor for appropriate measures.

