## 9. SAFETY AND TOLERABILITY

Safety and tolerability are evaluated by AEs, SAEs, clinical laboratory test results, body weight, vital signs, 12-lead ECG findings, and physical examination. All analyses of the safety data are performed using the safety analysis set. Descriptive statistics are presented by treatment group assignment in the safety analysis set. No formal statistical testing is performed for safety analyses. Safety is also summarized by a portion of the subgroups defined in Section 7.3. On-treatment values are summarized according to the analysis study windows in Section 5.5.3; off-treatment values are summarized according to the analysis study windows in Section 5.5.3.1. Safety data summaries are grouped by treatment.

Continuous safety parameters (including selected clinical chemistries and vital signs) may be summarized using the methodology described in Section 9.5.1 and Section 9.6. Only the visit windows outlined in Section 5.5.1 are included in these analyses.

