Summaries of UACR (Section 5.5.6) will use the geometric mean (with standard error) with 95% confidence intervals instead of the arithmetic mean and will display UACR results in original units of mg/g. Changes from baseline in UACR are calculated as the ratio of each visit to baseline and reported as the post-baseline/baseline ratios and are summarized by geometric means with 95% confidence intervals at each time point. Similar On Treatment MMRM analyses as described in Section 7.4.1 and the ANCOVA analysis described in Section 7.4.1.1, will be performed for UACR ratio to baseline. The change from baseline for UACR ratio to baseline at the protocol-defined endpoint time points Week 17 for patients treated with bardoxolone methyl compared to placebo may be performed using the ANCOVA models described in Section 7.4.1.1 and Section 8.1.1.1. Additionally, UACR is summarized by baseline UACR quartile. Summaries of UACR include values for scheduled visits.

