#### 9.5.1.1. Natural log(UACR)/eGFR

Mean ratios of natural log(UACR)/eGFR (Section 5.5.8) are summarized at each time point. The ratio of natural log(UACR)/eGFR by analysis visit is summarized by arithmetic means.

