#### 9.5.2. Categorical Summaries of Laboratory Results

Select laboratory parameters will be summarized using shift tables. Shift tables are summarized by treatment, laboratory category (hematology, chemistry, urinalysis, and microscopy), and laboratory test and present shifts from baseline status (Normal, Low, High) to worst on study treatment status (Normal, Low, High). The worst abnormality values are defined as the maximum values while on study treatment, with the exception of magnesium and hemoglobin. The worst abnormal values for magnesium and hemoglobin are defined as the minimum values while on study treatment.

Additionally, laboratory parameters of specific interest (ALT, AST, UACR) are summarized using shift tables that summarize shifts from (1) baseline status to end of treatment status, (2) worst on-treatment status to worst off-treatment status (3) worst on-treatment status to Day 35 off-treatment status, and (4) baseline status to worst on-treatment status (5) baseline to worst off-treatment, and (6) worst on-treatment status to best (lowest) off-treatment status. The number and percentage of patients are summarized. For UACR, summaries will present shifts from/to the categories listed in Section 5.5.6.1. For ALT and AST, summaries will present shifts from/to the following categories:

- $\leq$  ULN
- $>$  ULN to  $\leq$  3x ULN
- $>$  3x ULN

In addition, a summary table is provided for the number and percentage of patients meeting the following threshold levels at any time during the study:

- $>$  5x ULN for more than 2 weeks
- $>$  3x ULN and (TBL  $>$  2x ULN or INR  $>$  1.5)
- $>$  3x ULN with the appearance of fatigue, nausea, vomiting, right upper quadrant pain or tenderness, fever, rash, and/or eosinophilia ( $>$  5%).

- BNP > 200 pg/mL
- Magnesium < 1.3 mEq/L (0.65 mmol/L)
- NT-proBNP > 1000 pg/mL

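### ln(UACR)/eGFR does not adjust UACR for filtration: a UACR rise exactly proportional to eGFR reads as a fall of about 8–17%, and some doublings of UACR read as a fall

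*SAP*

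**What the plan says.** SAP 5.5.8 gives both the purpose and the form of the measure: "To evaluate UACR after adjusting for filtration rate, ln(UACR)/eGFR (Sections 5.5.6 and 5.5.5) is assessed". SAP 9.5.1.1 repeats the form and says how it will be reported: "The ratio of natural log(UACR)/eGFR by analysis visit is summarized by arithmetic means". The notation is the same in both sections, and neither gives a reason for the scale.

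The logarithm comes from SAP 5.5.6: "The UACR results are log-transformed for analysis to produce data that are more normally distributed". Nothing comparable is done to eGFR.

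UACR is also analysed without this adjustment. Under SAP 9.5.1, "Changes from baseline in UACR are calculated as the ratio of each visit to baseline and reported as the post-baseline/baseline ratios", with geometric means, 95% confidence intervals, MMRM and ANCOVA. Under SAP 9.5.2, "laboratory parameters of specific interest (ALT, AST, UACR) are summarized using shift tables". SAP 9 limits the standing of the safety summaries: "No formal statistical testing is performed for safety analyses".

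**The concern.** A filtration-adjusted UACR should stay constant when UACR and eGFR rise in the same proportion. Dividing a logged numerator by an unlogged denominator breaks this. A proportional rise in UACR moves ln(UACR) only slightly, while the same proportional rise in eGFR moves the divisor in full, so the UACR rise is under-weighted. Any filtration adjustment falls when eGFR rises at fixed UACR, and that is not the complaint. The complaint is that this one also falls when UACR keeps pace with eGFR, and sometimes when UACR doubles.

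This matters because both quantities are expected to move together on active drug. Protocol 5.1.2.6 says: "Therefore, increased eGFR, together with decreased megalin expression, is thought to result in decreased fractional absorption of albumin and increased urinary excretion of albumin". Whether albuminuria rises by more than filtration explains is therefore a natural safety question. The error arises mainly in the arm whose eGFR rises, so the table would tend to favour bardoxolone methyl and could disagree with the UACR analyses in SAP 9.5.1 and 9.5.2.

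**Working it through.** **Inputs**
- eGFR change d = +5.9 (Protocol 12.1).
- Eligible baseline eGFR 20 to <60 (inclusion criterion 2; SAP 5.5.6.2).
- UACR reference levels 30 and 300 mg/g (SAP Table 6) and 1000 mg/g (Protocol 9.1.6).
- Assumption: baseline values are chosen from these ranges, because the documents give no baseline distribution.

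The plan states no figure for this metric, so there is none to reproduce. The input 5.9 does fit the plan's own power statement: 35 × 0.85 = 29.75, about 30 completers per arm, and with SD 8 a two-sided t-test has 80.2% power against the stated 80% or so.

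**Notation.** U is baseline UACR, e is baseline eGFR, and k = 1 + d/e. The change in the metric is [ln(U′)/(e + d)] / [ln(U)/e] − 1, where U′ is follow-up UACR.

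**1. UACR rises in exact proportion to eGFR (U′ = kU; true adjusted change 0%)**

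The change is (1 + ln k/ln U)/k − 1.
- e = 55, U = 100: k = 1.107, giving (1 + 0.102/4.605)/1.107 − 1 = **−7.7%**.
- e = 25, U = 1000: k = 1.236, giving (1 + 0.212/6.908)/1.236 − 1 = **−16.6%**.
- Widest range, eGFR 20–59 and UACR 30–1000: −6.5% (e = 59, U = 30) to −19.9% (e = 20, U = 1000).

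The sign is general. Since ln k < k − 1, the metric falls for any eGFR rise whenever ln U > 1, that is, UACR above 2.72 mg/g.

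**2. UACR about doubles and eGFR rises 5.9**

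| UACR (mg/g) | eGFR | ln(UACR)/eGFR | Metric | UACR/eGFR |
|---|---|---|---|---|
| 300 → 600 | 40 → 45.9 | 0.1426 → 0.1394 | −2.3% | +74% |
| 600 → 1210 | 40 → 45.9 | 0.1599 → 0.1546 | −3.3% | +76% |
| 30 → 60 | 40 → 45.9 | 0.0850 → 0.0892 | +4.9% | +74% |
| 300 → 600 | 50 → 55.9 | 0.1141 → 0.1144 | +0.3% | +79% |

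The second row is a change of the size at which Protocol 9.1.6 says investigators "should closely monitor patients if urinary albumin to creatinine ratios increase by more than 100% and exceed 1000 mg/g".

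**3. When a doubling reads as a fall**

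(ln U + ln 2)/(e + d) < ln U/e rearranges to e < d × ln U/ln 2. For UACR 30, 100, 300, 600 and 1000 mg/g the cut-offs in baseline eGFR are about 29, 39, 48.5, 54 and 59. Above them the doubling reads as a small rise.

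**4. Arm means, every UACR doubling, every eGFR +5.9**

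Assume eGFR is uniform on (a, b) and independent of UACR, with geometric mean UACR G. Let R = ln((b + d)/(a + d))/ln(b/a). The mean metric changes by R × (ln G + ln 2)/ln G − 1.
- eGFR 20–60: R = 0.9339/1.0986 = 0.850. For G = 30, 100, 300 the change is +2.3%, −2.2%, −4.7%.
- eGFR 40–60: R = 0.3617/0.4055 = 0.892. The change is +7.4%, +2.6%, 0.0%.

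The geometric mean of UACR/eGFR rises 72% and 79% in these two settings.

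**5. Dependence on units**

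Protocol Appendix 1 equates 300 mg/g with 30 mg/mmol. At eGFR 30 → 35.9, a doubling from 300 mg/g reads −6.3%. The same doubling expressed from 30 mg/mmol reads +0.6%. A valid relative change cannot depend on the unit.

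**6. The alternative scale**

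With ln(U) − ln(e), the proportional rise gives exactly 0 at every baseline. A doubling with eGFR +5.9 gives a UACR/eGFR ratio to baseline of 2/k: 1.54 at eGFR 20, 1.67 at 30, 1.77 at 45 and 1.82 at 59. It is always a rise.

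**The case against.** **Little depends on the metric.** It has no hypothesis, interval, threshold or decision rule, and UACR is analysed properly alongside it. The Protocol 9.1.6 monitoring level acts on UACR directly, so this table cannot affect it. All of this stands, and it is why the point is minor.

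**The 8–17% belongs to a chosen grid.** This also stands. Over eGFR 20–59 and UACR 30–1000 the fall is about 6.5% to 20%. The sign does not depend on the grid.

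**The arm means ignore the planning SD of 8.** This is the strongest technical objection. The metric contains 1/eGFR, so spread in the eGFR change raises its mean. Simulating a normal SD of 8 (follow-up eGFR of 8 or less dropped) moves the active-arm changes to about +7%, +3% and 0% for eGFR 20–60, and about +10%, +5% and +2% for eGFR 40–60. Most of the within-arm falls disappear. But the same spread raises a placebo arm with no true change by about 6% and 3%. The active-to-placebo contrast, for example 1.00/1.06 − 1 ≈ −6%, is then about +1%, −3%, −6% and +7%, +2%, −1%. These are close to the figures without the spread, so the distortion between arms remains.

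**No document predicts that UACR will double or rise in proportion to eGFR.** This is true. Both are test cases for whether the measure does what SAP 5.5.8 says it is for. Proportionality is the neutral case for any per-unit-filtration measure. The percentage scale is also a choice made here, since SAP 9.5.1.1 plans mean ratios by visit, but the direction of change does not depend on it.

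**It may be only notation.** Possibly ln(UACR/eGFR) was meant. The text says otherwise in two sections, and a programmer following it would produce the faulty table.

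**Conclusion.** The concern holds, as a minor point. Followed exactly, SAP 5.5.8 and 9.5.1.1 produce a table that fails its own stated purpose. The core result needs no distributional assumption: at any UACR above 2.72 mg/g, a rise in UACR that exactly matches a rise in eGFR is reported as a fall. Its size does rest on assumed baselines and on the +5.9 planning change.

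A doubling of UACR reads as a fall chiefly at higher UACR and lower eGFR, and as a muted rise elsewhere. In every doubling case worked above, the metric hides a 67–79% rise in UACR per unit of filtration. The error tends to favour the arm whose eGFR rises.

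The primary endpoint, type I error and power are unaffected. An albuminuria signal would still be visible in the ratio-to-baseline analyses and shift tables. The risk is a misleading supplementary table that could contradict them.

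**What to change.** In SAP 5.5.8, replace ln(UACR)/eGFR with ln(UACR/eGFR) = ln(UACR) − ln(eGFR). In SAP 9.5.1.1, summarise its change from baseline at each visit, back-transformed to a geometric mean ratio to baseline with a 95% CI, so that it matches the UACR format in SAP 9.5.1 and can be read beside it. If this quantity was intended all along, correct the notation in both sections.

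The cost is one derivation line and one summary line. No new data are needed, because UACR and eGFR are already collected.

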#### **5.5.9. Trial Duration**

Trial duration is used in analyses of efficacy to calculate eGFR slope in the calculation of On-Treatment or Off-Treatment change in eGFR.

Trial duration used in the calculation of change in eGFR in the On-Treatment portion is the Week 12 or End of Treatment if discontinued early analysis visit date minus the date of the baseline assessment plus one.

Trial duration used in the calculation of change in eGFR in the Off-Treatment portion is the Week 17 date minus the date of the baseline assessment plus one. Note, the same baseline value will be used for both On-Treatment and Off-Treatment calculations.

### **5.5.10. eGFR Slope**

The eGFR slope for each patient will be calculated by dividing the change from baseline in eGFR (see Section 5.5.2) by the patient's On-Treatment trial duration (for the Week 12 primary endpoint) or Off-Treatment trial duration (for the Week 17 key secondary endpoint). Calculation of trial duration is described in Section 5.5.9.

## **5.6. Handling of Missing Data**

### **5.6.1. Missing Efficacy Endpoint Data**

#### **5.6.1.1. Missing eGFR for MMRM Analyses**

Missing eGFR data are not imputed for the primary, secondary and exploratory endpoint MMRM analysis (Section 7.4.1, 7.5.1 and Section 8.1). A set of sensitivity analyses is included to assess the robustness of conclusions (see Section 7.4.1.1, Section 7.5.1.1 and Section 8.1.1.1).

#### **5.6.1.2. Missing eGFR for ANCOVA Analyses**

In the subset of treatment-based multiple imputation sensitivity analyses, missing eGFR data is imputed based on an assumption of missing at random using multiple imputation based on the treatment group to which the patient is assigned. The analysis is performed using the ANCOVA statistical model defined in Section 7.4.1.1. In short, the PROC MI procedure in SAS is used to generate 100 datasets satisfying the assumption of monotone missingness, imputing any missing eGFR values using multiple imputation. Imputation is based on the non-missing observations within each treatment group. Seed specifications used in multiple imputation for sensitivity analyses of the primary endpoint and for sensitivity analyses of exploratory endpoints will be provided.

